We estimated a pre-defined 8-point non-inferiority margin, based on a significant effect of the COGNI-TRAcK in inducing an about 8-point mean increase at SDMT score (with respect to a sham intervention). Accordingly, 35 subjects per arm are required to ensure, with an approximately 85%-power level, that the lower limit of a one-side 95% confidence interval will be above the pre-defined non-inferiority margin. Therefore, considering also a drop-out rate of 25%, a total of 132 subjects should be enrolled.

Statistical methods

All analysis will be based on the intention-to-treat principle using the fully analysis dataset including all randomized patients. Missing data will be handled by multiple imputation method. Continuous data will be analyzed by parametric and non-parametric RM-ANOVAs with effect size estimation. The time-to-event data will be analyzed by Kaplan-Meier curves and Log-Rank test with a factor for treatment group.

An interim analysis will be conducted when at least 50% of the estimated sample size will complete the 8-week intervention period.

Study objectives

Primary objective	Primary endpoint
To demonstrate not inferior efficacy of exergames over COGNI-TRAcK and superior efficacy of both interventions over sham in improving sustained attention and information processing speed	Change at the SDMT from baseline to Week 8
Secondary objectives	Secondary endpoints
To demonstrate not inferior efficacy of exergames over COGNI-TRAcK and superior efficacy of both interventions over sham in improving cognitive functions	Change at the BICAMS and SCWT from baseline to Week 8
Additional objectives	Additional endpoints
To demonstrate not inferior efficacy of exergames over COGNI-TRAcK and superior efficacy of both interventions over sham in reducing the impact of MS on: - cognitive-motor interference - activities of daily living - fatigue - work productivity	Change of dual-task cost of walking and balance as estimated by the 2MWT and static posturography in dual-task vs. single-task condition from baseline to Week 8 Change at the MSIS-29 from baseline to Week 8 Change at the MFIS from baseline to Week 8 Change at the WPAI:MS from baseline to Week 8
Exploratory objectives	Exploratory endpoints
To demonstrate not inferior efficacy of exergames over COGNI-TRAcK and superior efficacy of both interventions over sham on: - physical activity - adherence	Physical activity measured by wearable actigraph Percentage of training completed at home

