A recent meta-analysis exploring the role of exergames in improving cognitive functions in persons suffering from neurological disabilities (including MS), showed that exergames significantly improved executive functions and visuo-spatial perception when compared to alternative or no intervention [22]. Therefore, exergames can represent a highly-flexible tool to rehabilitate both cognitive and motor functions by means of an unique training.

COGNI-TRAcK is a low-cost, user-friendly application software (app) for portable devices (mobile phone and tablet) that delivers a self-administered, intensive and monitored cognitive training based on working memory exercises. The main feature of COGNI-TRAcK is the implementation of automatic adaptive working load algorithms and procedures for intensiveness regulation. Moreover, it can be easily used at home enhancing the possibility to schedule an intensive training and ensuring adherence to treatment. Preliminary data showed that COGNI-TRAcK is highly usable, motivating and well-accepted by patients with MS [25]. Adaptive COGNI-TRAcK (i.e. automatic adjustment of tasks difficulty) has been found superior over sham COGNI-TRAcK (i.e. constant difficulty level) in verbal memory acquisition and delayed recall, verbal fluency, sustained attention, concentration and information processing speed [24]. Therefore, sham COGNI-TRAcK can be used as placebo-analogue arm in order to avoid ethical concerns and a possible unmotivating effect of wait-list group.

Rationale for study endpoints

The SDMT (primary endpoint) represents a simple screening test for cognitive impairment [26],[27]. An improvement of 4 points or 10% in magnitude is considered clinically relevant [28].

The Brief International Cognitive Assessment for MS (BICAMS) (secondary endpoint) has been recently developed as brief, practical and universal assessment tool for cognitive impairment in MS; it includes the SDMT, the California Verbal Learning Test-2 (CVLT2) and the Brief Visuospatial Memory Test–Revised (BVMT-R) [29]. To test some aspects of executive functions not explored by the BICAMS, the Stroop Color-Word Test (SCWT) is also included in the assessment [30].

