Measurements of Cognitive-Motor Interference (CMI) and Patient-Reported Outcomes (PROs) for assessing activities of daily living, fatigue and work productivity (additional endpoints), as well as measurements of physical activity by actigraph and adherence to protocol (additional endpoints) provide data to evaluate the extent to which an improvement in primary and secondary endpoints can be transferred into real world activity (i.e. ecological validity) and acceptability for patients.

Occurrence and timing of adverse events (AEs), with particular attention for accidental falls, provide data on safety of home-based, minimally assisted interventions.

Risk:benefit ratio and ethical consideration

Cognitive dysfunction and motor impairment are disabling symptom in people with MS across all disease stages. The present study will test the efficacy and safety of a novel rehabilitation approach that can be used in a home care setting for exploiting and promoting – by using a single training session – the combined motor and cognitive function of specific brain regions using exergames.

Results from published studies indicated a positive risk:benefit ratio for exergames, with no or only minor AEs [9]. Pilot studies with home-based exergames have reported indeed no increased risk of accidental falls and only minor musculo-skeletal problems solved with training discontinuation or at least standard treatment [9]. No AE or side effects are reported for home-based COGNI-TRAcK. Therefore, low-cost, commercial, minimally supervised exergames can potentially offer a cost-efficacy profile at least equal (or even better, as previously reported) than standard rehabilitation care, through the reduction in transport and staffing costs [11].

METHODS

[figure not shown]
Study design

This is a phase II, multicenter, randomized, sham-controlled, single-blind, parallel group, multicenter study to test the hypothesis that home-based exergames is not inferior to home-based cognitive rehabilitation delivered by a software application (app) for mobile devices and both interventions are superior to a placebo-analogue intervention in improving cognitive function and reducing cognitive-motor interference in people with MS.

Participants

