Exploratory endpoints: the MSIS-29 is a self-administered questionnaire measuring physical and psychological impact of MS from the subject's perspective; it has been reported to be more sensitive than other quality of life scales in detecting rehabilitation-induced changes [43]. The MFIS-21 is a self-administered questionnaire based on items derived from interviews with subjects with MS concerning how fatigue impacts their lives; it comprises three subscales (physical, cognitive, and psychosocial functioning) [44]. The WPAI:MS questionnaire measures employment status, absenteeism, impairment during work, overall work impairment and daily activity impairment [45].

Adherence

All eligible patients will receive a logbook to daily record the log of training (including time and type of game played). The logbook will be given at baseline visit and will be returned to the treating operator at the end of the training period (Week 8 visit). The machine log included in all the devices used in the present study allows double-check of adherence to intervention protocol.

Safety

Patients will be encouraged to contact the treating operator or another component of the study team (excluding the assessing operator) in case of AEs, for any question regarding the study protocol or technical problems. All eligible patients will receive a patient diary to record any AE occurring during the study and the occurrence of accidental falls, defined as an unexpected contact of any part of the body with the ground that not results from loss of consciousness. The patient diary will be given at baseline visit and will be returned to the treating operator at the end of the follow-up period (Week 16 visit).

AEs will be reported according to the World Health Organization (WHO) guidelines for Good Clinical Practice (GCP) in biomedical research on human subjects [46]. AEs are graded as mild (minimal or no treatment required and no interference with daily living activities), moderate (may require treatment and cause some interference with functioning), severe (systemic drug or other treatment required, interruption of daily living activities), or life-threatening (immediate risk of death).

Predictors of outcomes

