For the superiority comparison, the null hypothesis is that the intervention with adaptive COGNI-TRAcK is not superior to sham COGNI-TRAcK, while the alternative hypothesis is that the intervention with adaptive COGNI-TRAcK is superior to sham COGNI-TRAcK in increasing the proportion of responders as afore defined. Enrolling 35 patient per arm will ensure a more than 95% power in detecting a statistical significance between-group difference of 50% at two-sided alpha level of 5%.

Statistical analysis

All analysis will be based on the intention-to-treat principle using the fully analysis dataset including all randomized patients. Missing data will be handled by multiple imputation method, with the assumption that some data will be missed completely at random.

Efficacy analyses: efficacy data will be analyzed by parametric and/or non-parametric Repeated Measures Analyses of the Variance (RM-ANOVAs) with effect size estimation. In each analysis, we will consider as dependent variable all measures or score derived from study assessments; the three study visits (Baseline, Week 8 and Week 16) as within-subject factors; and intervention arms (exergames, adaptive COGNI-TRAcK and sham COGNI-TRAcK) as between-subject factors. Effect sizes will be estimated as Cohen's F-squared, rated as small, medium, and large for values of 0.02, 0.15, and 0.35, respectively [54].

Safety data regarding time to first accidental falls will be analyzed as time-to-event data by Kaplan-Meier curves and Log-Rank test with a factor for intervention arms.

Safety analyses: data regarding the occurrence of adverse events during the intervention period and the follow-up period will be analyzed by the Chi-squared test comparing the independent distribution of events according to intervention arms.

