Predictors of outcomes: logistic regression analyses will test if the achievement of a clinically relevant change in the pre-planned endpoints is predicted by scores derived from CRIQ, HLAQ and TCI, after controlling for a set of baseline covariates including sex, age, disease duration, EDSS score, performance on the explored task. For those endpoints lacking of a definition of clinically relevant change, we will adopt Analyses of Covariance (ANCOVAs) with immediate post-training score as dependent variables, intervention arm as fixed factor and a set of baseline covariates including sex, age, disease duration, EDSS score, baseline performance on the explored task, as well as scores derived from CRIQ, HLAQ and TCI as covariates of interest.

Pre-planned statistical significance level

Exergames and adaptive COGNI-TRAcK will be compared with sham COGNI-TRAsK as placebo-analogue arm. Therefore, all analysis will be corrected with Bonferroni adjustment for multiple comparisons of two-sided tests, giving a two-sided significant p-value of 0.025.

Interim analysis

An interim analysis will be conducted when at least 50% of the estimated sample size will complete the 8-week intervention period.

STUDY GOVERNANCE AND OVERSIGHT

Steering committee

The steering committee shall comprise the Principal Investigator (PI) and all the co-investigators reported in this study protocol.

The steering committee will be responsible for the overall design, interpretation, supervising and reporting (presenting at national and international congresses and publishing in peer-reviewed journals). Members of steering committee will be also responsible for providing clinical guidance on study implementation and conduct in their respective sites.

Data Monitoring

An independent Data Monitoring Committee (DCM) will be appointed to review the overall conduct of the study, with particular attention to eligibility criteria, randomization, and collection of efficacy and safety data. The DCM will have access to the individual treatment codes while the study is ongoing; therefore, if DMC expresses safety concerns, appropriate information will be sent to the PI, regulatory authorities and study funder Associazione Italiana Sclerosi Multipla (AISM).

The DCM is also responsible for ensuring the maintenance of blinding and integrity of the study.

ETHICAL AND REGULATORY REQUIREMENTS

Ethical conduct of the study

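### The 0.025 significance level corrects only for the two sham contrasts within one endpoint, yet the objectives set out to demonstrate superiority over sham on ten endpoints beyond the SDMT, with no hierarchy

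*Protocol*

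**What the plan says.** Under *Pre-planned statistical significance level*, the protocol notes that both active arms are compared with sham and concludes that "all analysis will be corrected with Bonferroni adjustment for multiple comparisons of two-sided tests, giving a two-sided significant p-value of 0.025". The count of two active arms is the only reason given for the divisor.

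The *Study objectives* table in the synopsis uses the same verb, to demonstrate, in all four efficacy tiers:

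- The secondary objective is "superior efficacy of both interventions over sham in improving cognitive functions", measured by BICAMS and SCWT.
- The additional objective is "superior efficacy of both interventions over sham in reducing the impact of MS on" cognitive-motor interference, daily activities, fatigue and work. Its endpoints are two dual-task costs, MSIS-29, MFIS and WPAI:MS.
- The exploratory objective covers physical activity and adherence.

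Under *Statistical analysis*, the efficacy paragraph applies one repeated-measures analysis to everything: "we will consider as dependent variable all measures or score derived from study assessments".

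Two further statements bear on the tiers. *Rationale for study endpoints* says of the BICAMS that "it includes the SDMT", which is the primary endpoint. Tier labels also differ between sections. *Rationale for study endpoints* places the patient-reported outcomes in the additional tier, and likewise the actigraph and adherence: "as well as measurements of physical activity by actigraph and adherence to protocol (additional endpoints". *Study assessments, Efficacy* has instead "Exploratory endpoints: the MSIS-29 is a self-administered questionnaire" and goes on to list MFIS and WPAI:MS there.

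**The concern.** Halving 0.05 for two contrasts protects one endpoint. It gives no protection across endpoints, and the objectives ask for demonstrated superiority on many of them. No text makes a lower-tier claim depend on the SDMT result. If the trainings do nothing, the plan can still yield a nominally demonstrated benefit on some memory, dual-task, quality-of-life, fatigue or work measure, and a reader could not tell it from a confirmatory result.

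The tier labels offer little shelter. The exploratory tier is also worded as a demonstration at the same level, and the sections disagree about which endpoints belong to it. Because BICAMS contains the SDMT, one SDMT result could be presented as both a primary and a secondary success.

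**Working it through.** **Inputs from the protocol**

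- Significance level for every analysis: two-sided 0.025 (*Pre-planned statistical significance level*).
- Contrasts per endpoint: 2, sharing one sham arm; 1:1:1 allocation.
- Endpoints beyond the SDMT (synopsis): 3 secondary (CVLT2, BVMT-R, SCWT) + 5 additional (dual-task cost of walking, dual-task cost of balance, MSIS-29, MFIS, WPAI:MS) + 2 exploratory (physical activity, adherence) = 10. Counting BICAMS once gives 9; testing subscales separately gives more.

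**Assumption:** the protocol gives no correlation between endpoints, so it is varied from 0 to 0.8.

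**The plan's own figure.** 0.05 / 2 = 0.025, as stated. For one endpoint, two independent tests would give 1 − 0.975² = 4.9%. With the shared sham arm (contrast correlation 0.5), simulation gives about 4.7%. The rule does its job within one endpoint.

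**Across endpoints.** The ten endpoints give 10 × 2 = 20 tests. As an upper reference, if all 20 were independent, 1 − 0.975²⁰ = 39.7%.

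For dependent tests I simulated three equal arms with a common between-endpoint correlation. Each contrast is z = (active − sham)/√2, and a test rejects when |z| > 2.241. All nulls are true, with 400,000 draws per setting.

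| Endpoints | Correlation | Any rejection, either direction | Any rejection favouring training | Both arms beat sham on the same endpoint |
|---|---|---|---|---|
| 1 | – | 4.7% | 2.3% | 0.2% |
| 3 secondary | 0 | 13.3% | 6.8% | 0.5% |
| 3 secondary | 0.5 | 11.9% | 6.0% | 0.5% |
| 3 secondary | 0.8 | 9.4% | 4.7% | 0.4% |
| All 10 | 0 | 37.9% | 20.9% | 1.8% |
| All 10 | 0.5 | 27.8% | 14.0% | 1.4% |
| All 10 | 0.8 | 17.0% | 8.5% | 0.9% |

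**When one arm truly works.** The last column assumes that neither arm works. Suppose one arm has a large effect on all ten endpoints and always beats sham. A false claim for both arms then needs only one false favourable result for the other arm, at one-sided 0.0125 per endpoint. With independent endpoints this is 1 − 0.9875¹⁰ = 11.8%. By simulation it is 11.7% at correlation 0, 8.0% at 0.5 and 4.8% at 0.8, or about 5% to 12%.

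**Tier labels side by side**

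| Endpoint | Synopsis | Rationale for study endpoints | Study assessments, Efficacy |
|---|---|---|---|
| MSIS-29, MFIS, WPAI:MS | additional | additional (as patient-reported outcomes) | exploratory |
| Actigraphy, adherence | exploratory | additional | not tiered |
| SDMT | primary, and secondary through BICAMS | primary, and secondary through BICAMS | primary, and secondary through BICAMS |

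**The case against.** This is a phase II trial with one named primary endpoint. Strict error control across lower tiers is often not required, and testing order is commonly left to an analysis plan, which is not shown. That limits the severity. It does not remove the point, because the protocol is not silent: it fixes one level for every analysis and words every tier as a demonstration.

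A stronger argument is that the objectives speak of both interventions beating sham. Read as a joint requirement, the false-claim chance is only about 1% to 2% when nothing works. Two things weaken this defence. A Bonferroni split is needed only if either contrast alone can support a claim, and the sample-size section states its superiority hypothesis for adaptive COGNI-TRAcK alone. The joint reading also loses its protection once one arm works, when the chance rises to about 5% to 12%.

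A reader might infer a single figure of about 28% for a false superiority claim. The protocol does not support that. The figure needs an assumed correlation of 0.5, and it counts results in which sham beats training; at that correlation the benefit-only figure is about 14%.

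The count of ten can also be disputed, since adherence is hardly an efficacy outcome. The calculation further assumes pairwise tests that do not depend on a significant omnibus result, which the protocol does not settle. Relabelling tiers would by itself change no error rate while every tier is tested at 0.025. The overlap of SDMT and BICAMS follows from the battery's definition; it creates an opportunity for double counting and does not show that this is intended.

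**Conclusion.** The point holds, as a matter that should be corrected and not as a fatal flaw. The 0.025 level controls error within an endpoint, while the protocol promises demonstrations on ten more endpoints without any ordering.

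The size depends on what counts as a claim. If one contrast suffices and all nulls are true, the chance of a significant result in either direction is about 17% to 38%, and of a false benefit 8.5% to 21%. For the three secondary tests alone the false-benefit figure is 4.7% to 6.8%, against about 2.3% for one endpoint, so most of the inflation comes from the lower tiers. A joint claim is protected when neither arm works and much less so when one does. All these figures rest on an assumed equal correlation between endpoints.

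The conflicting tier labels and the SDMT's presence in two tiers are plain textual inconsistencies and need no assumption.

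**What to change.** 1. In *Pre-planned statistical significance level*, state that the 0.025 level supports confirmatory superiority claims on the SDMT only.
2. In the synopsis, reword the additional and exploratory objectives from demonstrating to exploring. Report them with estimates and nominal confidence intervals, and make no claim of demonstrated superiority.
3. Treat CVLT2, BVMT-R and SCWT in the same way. If confirmatory claims on them are wanted, test them only after the corresponding SDMT contrast with sham succeeds, using Holm or a fixed order at 0.025 within that contrast. Gating is one acceptable option and not the only correct one.
4. Name CVLT2 and BVMT-R in place of BICAMS as secondary endpoints, so that the SDMT sits in one tier.
5. Give each endpoint one tier and use it consistently in the synopsis, *Rationale for study endpoints* and *Study assessments*.

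The cost is wording only, with no extra patients, visits or data. The price is that lower-tier endpoints carry no confirmatory claim, or that the three secondary tests face a stricter threshold.

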No pharmacological treatment is strictly forbidden; however, patients are encouraged to not start pharmacological treatments that can potentially impact on cognition, namely antidepressants, dalfampridine, nabiximols, modafinil, amantadine, dopamine-agonists.

Steroid administration due to MS relapse or any symptomatic drug initiation due to any MS-related symptom should be considered as an AE.

Patients are encouraged to not start any other type of physiotherapy or rehabilitation during the study period, but they are encouraged to continue his/her physiotherapy or rehabilitation program if started at least 3 months before the study enrolment.

STATISTICAL PLAN

Sample size estimation

Overall, we will randomize **126 patients** (considering even a 20% drop-out rate), based on two previously published studies that have found:

- (i) a significant effect of an home-based cognitive training using the [name]® Brain Training that promoted an about 8-point mean increase at SDMT score (with respect to wait-list group) [53];
- (ii) a significant effect of adaptive COGNI-TRAcK that promoted an about 8-point mean increase at SDMT score (with respect to a sham intervention) [24];
- (iii) a 50%-difference in proportions of responders (10/14 versus 3/14 in adaptive COGNI-TRAcK group and sham COGNI-TRAcK group, respectively) [24], according to a responder definition of SDMT change approximating 4 points or 10% in magnitude [28].

For the non-inferiority comparison, the null hypothesis is that the intervention with exergames is inferior to adaptive COGNI-TRAcK, while the alternative hypothesis is that the intervention with exergames is non-inferior to adaptive COGNI-TRAcK by a pre-defined amount of SMDT score.

If there is truly no difference between exergames and adaptive COGNI-TRAcK, then 35 patients per arm are required to ensure, with a statistical power of approximately 85%, that the lower limit of a one-sided 95% confidence interval (or equivalently a 90% two-sided confidence interval) will be above the predefined non-inferiority margin of 8-point change in SDMT.

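### Single-step Bonferroni at 0.025 for the two SDMT contrasts with sham is valid, but Holm's step-down would give the same 5% error control and never reject less

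*Protocol*

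**What the plan says.** The primary objective in the synopsis (Study objectives) joins two claims on SDMT change to Week 8: non-inferiority of exergames to COGNI-TRAcK, and "superior efficacy of both interventions over sham in improving sustained attention and information processing speed".

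The section on the pre-planned statistical significance level says "Exergames and adaptive COGNI-TRAcK will be compared with sham COGNI-TRAsK as placebo-analogue arm" and then fixes the rule: "all analysis will be corrected with Bonferroni adjustment for multiple comparisons of two-sided tests, giving a two-sided significant p-value of 0.025". The protocol gives no step-down, hierarchical or joint-success rule.

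The sample size section powers superiority for adaptive COGNI-TRAcK against sham only, on responder proportions: "Enrolling 35 patient per arm will ensure a more than 95% power" for a "between-group difference of 50% at two-sided alpha level of 5" per cent. The rates behind it are "10/14 versus 3/14 in adaptive COGNI-TRAcK group and sham COGNI-TRAcK group, respectively". The same section cites "a significant effect of adaptive COGNI-TRAcK that promoted an about 8-point mean increase at SDMT score (with respect to a sham intervention"). It states no SD for SDMT change.

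**The concern.** The adjustment covers exactly two contrasts that share the sham arm. Single-step Bonferroni holds the second contrast to 0.025 even after the first has been rejected. At that stage at most one null hypothesis can still be true, so testing it at 0.05 would keep the family-wise error at 5%. The stricter level therefore buys no extra error control. It lowers the chance of showing what the objective states, that both trainings beat sham. The protocol gives no power for that joint result.

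**Working it through.** **1. The plan's own figures.** 0.05 / 2 = 0.025, as stated. Superiority power for 10/14 = 71.4% against 3/14 = 21.4% with 35 per arm at two-sided 5% is 99.5% (98.5% by Fisher's exact test), which agrees with the stated figure of more than 95%. At 0.025 it is 98.8% (97.1% by Fisher's exact test).

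**2. Rules compared.**
- Bonferroni shows both if both p-values are ≤ 0.025.
- Holm shows both if the smaller p is ≤ 0.025 and the larger is ≤ 0.05.
- An unadjusted joint rule shows both if both are ≤ 0.05.

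Bonferroni and Holm show at least one in exactly the same cases (smaller p ≤ 0.025). Under the global null with correlation 0.5, the family-wise error is 4.6% for both.

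**3. Which SD?** None is stated, so these are assumptions.
- From the non-inferiority statement ("35 patients per arm are required to ensure, with a statistical power of approximately 85" per cent, margin 8, one-sided 5%): SD = 8 × √(35/2) / (1.645 + 1.036) = 12.48 by the normal formula, or 12.36 with the t distribution. Call it about 12.4.
- From the section on the rationale for design and duration, which reports the 8-point difference with p < 0.001. If that came from an ordinary two-sample t-test with 14 per arm, SD ≤ 8 / (3.707 × √(2/14)) = 5.7.

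**4. SDMT means.** Effect 8 points in both active arms, 35 per arm, noncentrality 8 / (SD × √(2/35)), correlation 0.5 from the shared sham arm and 1:1:1 allocation, pooled-variance t with 102 df, simulated.

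| SD | Both, Bonferroni | Both, Holm | Gain (points) |
|---|---|---|---|
| 5.7 | 99.96% | 99.99% | 0.0 |
| 7 | 98.8% | 99.5% | 0.7 |
| 8 | 94.7% | 97.2% | 2.5 |
| 9 | 87.1% | 92.2% | 5.1 |
| 10 | 76.8% | 84.6% | 7.8 |
| 12.36 | 51.9% | 62.9% | 11.0 |

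Over all effect sizes at correlation 0.5, the largest gain is 11.1 points (10.9 when the two effects are equal, by the normal approximation). The unadjusted joint rule reaches 64.1% at SD 12.36.

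**5. One given contrast.** With equal effects the gain is at most about 5.5 points: 66.7% to 72.2% at SD 12.36, 85.7% to 89.6% at SD 10, and 92.4% to 95.0% at SD 9.

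**6. Responder rates.** With 71.4% in both active arms against 21.4%, the chance of showing both rises from 97.2% to 98.5%, a gain of 1.4 points from the unrounded values. If exergames reached only 50% responders (assumption), it rises from 61.9% to 72.1%, a gain of 10.2 points.

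**The case against.** The strongest reply is that nothing here is wrong. Bonferroni is valid under any correlation, 0.025 is correctly derived, and the rule is fixed in advance. That stands. A reader might infer that the protocol's multiplicity control is defective, and the documents do not support that.

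A reader might also infer that the trial gives up 11 points of power. That figure is about the maximum. It needs an SD near 12.4, which is only backed out of the non-inferiority statement. The reported p < 0.001 points to a much smaller SD, where the gain is close to zero, and the superiority calculation itself rests on responder rates where the gain is 1.4 points. Using 35 per arm also leaves out patients beyond the evaluable minimum. With 126 randomized, or 42 per arm, and full information, the gain at SD 10 is 5.5 points (86.0% to 91.4%, from unrounded values). These limits stand, though neither source of a small gain is firm. The p-value reading assumes a particular test, and the responder rates come from 14 patients per group and say nothing about exergames.

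Finally, the word both in the objective might be read as a strict requirement that both trainings win. If so, no adjustment would be needed and Holm would not be the natural remedy. The protocol adjusts for two comparisons and states no joint-success rule, so it does not settle this. Holm is the right replacement if each training may also be claimed alone.

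**Conclusion.** The single-step rule is valid but less powerful than it need be. Replacing it with Holm for the two SDMT contrasts leaves the 5% error control unchanged and can only add rejections.

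The gain in showing both ranges from about 0 to 11 points, depending on the unstated SD and on equal 8-point effects with 35 per arm. Near-zero gain is as compatible with the protocol's figures as the maximum. The probability of at least one success is the same under either rule.

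This is an efficiency point of modest weight, worth making because the change is so small.

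**What to change.** For the two SDMT contrasts with sham, replace the Bonferroni sentence with: Holm's step-down at family-wise two-sided 5%; the smaller p-value is tested at 0.025 and, if it is significant, the other at 0.05. The non-inferiority comparison is not affected by this change.

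If the sponsor will claim success only when both trainings beat sham, state that instead and test each contrast at two-sided 0.05 without adjustment.

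The cost is one sentence, with no extra patients or visits. The one drawback is that simultaneous confidence intervals matching Holm are less simple; 97.5% intervals can still be shown. The choice should be fixed before any comparative data are seen, and so before the planned interim analysis.
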